5.3.1.1 Reporting of Adverse Events

All AEs, regardless of severity and whether or not they occurred during the study treatment or within 21 days following the last treatment, are to be documented by the Investigator appropriately, including date of onset, severity, action taken, outcome, and relationship to study drug. Adverse events occurring between the time of signing informed consent to the time of the first dose will NOT be captured as AEs unless the AE is a direct result of a study-specific procedure or results in death from an event other than PD.

The Data and Safety Monitoring Plan of the Brown Cancer Center will be used for this phase I/II protocol. The investigators will conduct continuous review of data and patient safety at weekly meetings where the results of each patient’s treatment are discussed. The discussion will include the number of patients, significant toxicities as described in the protocol, dose adjustments, and responses observed. Quarterly summaries of SAEs will be submitted through the CTO to the DSMC for review.

In the case of an SAE, the Investigator must notify the Co-Chairman of the Data Safety Monitoring Committee within 24 hours of becoming aware of the event, and will notify the Institutional Review Board in accordance with its guidelines.

5.3.2 Laboratory Assessments. At Day 1 of each cycle, a CBC with a 3-part differential and a CMP will be ordered and assessed by the Investigator.

6. STATISTICS

6.1 Study Design:

The study will be a single-arm, single center, uncontrolled phase I/II trial to estimate the safety of the combined treatments and then estimate the efficacy in terms of objective response (CR+PR) rate in patients with stage IIIC and Stage IV melanoma treated with dabrafenib/trametinib and metformin.

6.2 End-Point Definitions:

We will use two main end points. The primary endpoint of interest is the clinical response as defined in Section 5. The second end point will be tolerability to treatment. Secondary end points to be considered are the overall survival, OS, which is the time to first event or death due to any reason.

6.3 Sample Size:

The study is conducted in 2 phases.

Phase I:

In phase I, we will enroll 6 patients for the combination regimen of Dabrafenib/Trametinib/Metformin. We will allow at the most two drug-related CTCAE grade 4 toxicities in 6 patients in order to advance to Phase II. If we observe any drug-related deaths or more than two drug-related CTCAE grade 4 events, then we will halt the trial.

The Data and Safety Monitoring Plan of the Brown Cancer Center will be used for this phase I/II protocol. The investigators will conduct continuous review of data and patient safety at weekly meetings where the results of each patient's treatment are discussed. The discussion will include the number of patients, significant toxicities as described in the protocol, dose adjustments, and responses observed. Quarterly summaries of SAEs will be submitted through the CTO to the DSMC for review.

Phase II:

There is no data available at the institution to support the sample size justification based on efficacy of this treatment combination. **In the published literature, the objective response rate to Dabrafenib and Trametinib using RECIST 1.1 Criteria is 76% (N=54, 95% CI, 65% to 87%)¹ (Flaherty et al, NEJM, 367:1694, 2012).** We expect that the overall response rate should be between 60-80%. Therefore an objective response rate less than 64% should indicate the treatment is not sufficiently promising ($P_0 = 0.64$); this is a bit lower than the lower limit of the 95% CI. We expect the therapy to increase the overall response rate at 80% ($P_1 = 0.80$). Using Simon's two stage minimax design for phase II trials we plan to enroll a maximum of 53 patients. In first stage, 20 patients will be enrolled. Table S1 gives the details of the justification of this sample size. Note that if the treatment is not altered in Phase I, patients enrolled on Phase I will be included in Phase II in the efficacy estimation.

Table S1. Sample size justification $P_0 = 0.64$, $P_1 = 0.80$, $\alpha = 0.05$ and power = 80%

MiniMax Two Stage Design	MiniMax Design
First Stage Sample Size (n1)	20
Upper Limit For 1 st Stage Rejection of Drug (# of OR)	13
Maximum Sample Size (n)	53
Upper Limit for 2 nd Stage Rejection of Drug (# of OR)	39
Expected Sample Size If Response Probability = 0.64	33
Probability of Early Termination at If RP=0.64	0.62

6.4 Accrual Rate:

Based on our experience we plan to enroll 30 patients per year. It will take approximately 2.0 years to complete the enrollment of 53 patients. Depending on the treatment's performance we may not need to enroll all 53 participants. Given the relatively short overall survival times, all patients will be followed for up to 3 years once enrolled and after the end of treatment with Dabrafenib/Trametinib/Metformin.

6.5 Statistical Analysis:

General Approach:

Patients receiving treatment will be presented. Patients receiving treatment who are found not to have fully met the eligibility criteria will be presented. On-study protocol violations will also be presented. Patients who do not complete the required observations will be listed and evaluated separately as necessary. Reasons for study discontinuation and date of withdrawal from study will be presented.

Descriptive statistics related to the participant characteristics, treatment, and prognostic factors will be reported. Clinical response rates (complete, partial, and sustained) along with 95% confidence intervals will be estimated. The overall survival will be estimated by the Kaplan-Meier method²⁹. Differences in survival will be evaluated through the estimated hazard rates using the un-weighted log-rank tests. The OS time will be determined as the time from enrollment until death or last follow-up evaluation. In order to examine the significant prognostic factors, we will use the Cox proportional hazards regression models in both uni-variable and multi-variable setting³⁰. Descriptive statistics associated with the toxic events will be reported. The factors to be analyzed are ethnicity, gender, age, and pathological subtype. The various factors will be placed into categorical variables.

All calculations will be performed with SAS statistical software (SAS Institute Inc., Cary, NC). Analyses for specific aims are outlined below.

Statistical Analysis for specific aims:

Primary Objectives:

- *To evaluate the safety of the FDA-approved Dabrafenib and Trametinib in combination with Metformin in patients with unresectable Stage IIIC and Stage IV melanoma (Phase I).*

A total of 6 consecutive patients will be evaluated on this combination treatment. If any drug-related death occurs in this early stage, the study will be suspended. To continue on Phase II, at the most two drug-related CTCAE grade 4 events are allowed, which is in line with a Typical Phase I study with only one dose.

- *To estimate the efficacy of the Trametinib/Dabrafenib/Metformin regimen (Phase II).*

The efficacy will be estimated based on objective response (OR) rate, which is PR+ CR. We will estimate the OR rate along with its 95% confidence interval. We will also estimate CR and PR rates along with 95% confidence intervals. We will also compare these rates with published rates NEJM (2011)⁸ by comparing the confidence intervals.

- *To monitor the safety the combined regimens (Phase I/II).*

The monitoring rule is outlined in the next subsection.

Secondary Objective:

- *To estimate the overall survival rate on the combined regimes.*

We will estimate the overall survival (OS) rates using the method of Kaplan-Meier. To compare the results with historical controls (results published in NEJM, 2011 and others), we need to estimate fixed term (such as 1-year, 2-year) OS rate along with 95% confidence interval precisely, that we plan to do using the method of Yuan and Rai (2011)³¹

- *To describe the toxicities.*

We will produce frequency and percentages of different CTCAE.

- *To explore the effect of other covariates (demographic, disease and treatment related) on objective response rate and toxicity and overall survival.*

We will identify the covariates and define specific groups, using some cut-offs, that are meaningful in a regression analysis. The effect of the covariates on a dichotomous outcome (OR or Toxicity) and time-to-event (OS) will be explored using a logistic regression and Cox proportional Hazards model, respectively.

6.6 Monitoring Rule for Phase II:

Safety monitoring of the accumulated outcomes data is designed to ensure the continuing safety of the currently enrolled participants and participants not yet enrolled. This is achieved by stopping the trial early to reduce the number of participants exposed to a harmful or ineffective treatment.

6.7 Non-efficacious Treatment (Futility):

In the combined regimen Dabrafenib/Trametinib/Metformin: in the first stage we will enroll 28 participants and if we observe at most 12 objective responses we will not enroll any new participants. If we observe 13 or more objective responses in the first stage, then we plan to enroll an additional 25 patients. In order for the treatment to be declared effective there has to be objective responses in at least 29 patients. If the objective response rate is only 41%, we will have 66% chance of stopping the study early and, at most, 37 patients will be treated on the potentially ineffective therapy.

6.8 Toxic Treatment (Safety) for Combined Phase I/II Trial:

The cumulative number of grade 3 or 4 toxic events will be monitored after each person is enrolled^{32, 33}. If the cumulative number of toxic events produces enough evidence to conclude that the true toxicity rate is greater than or equal to 33% ($Pt_0 = 0.33$) then the trial will be stopped early for safety reasons. The cumulative number of toxic events after each person is treated will be compared to the boundary values in Table S2. If the cumulative number of toxic events after person is treated is greater than or equal to the associated boundary value b_i then the combination treatment is rejected for safety considerations. With this rule, there is only a 5% chance of stopping the trial early for lack of safety if the true toxicity rate is less than 33%. Continual assessment of the toxic events ensures we do not expose an undue number of patients to a harmful treatment.

Table S2. Toxicity Boundaries, $N = 53$, $Pt_0 = 0.33$, and $\alpha = 0.05$

Minimum Number of Subjects	Maximum Number of Subjects	Number of Toxicities
4	4	4
5	6	5
7	7	6
8	9	7
10	11	8
12	14	9
15	16	10
17	18	11
19	19	12
20	22	13
23	23	14
24	27	15
28	28	16
29	30	17
31	32	18
33	34	19
35	37	20
36	40	21
41	42	22
43	45	23
46	47	24
48	50	25
51	52	26
53	54	27

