Diagnosis and entry criteria:	
Exclusion Criteria
 
Patients will not be entered in the study for any of the following:
 
 1. Prior treatment with Vemurafenib or Dabrafenib 2. Known hypersensitivity to Metformin or any of its components; 3. Received radiotherapy for non CNS disease within the 2 weeks prior to commencing study treatment or have not recovered from side effects of all radiation-related toxicities to Grade ≤ 1, except for alopecia; 4. Pregnant, breast-feeding, or refusing double barrier contraception, oral contraceptives, or avoidance of pregnancy measures; 5. Have any other uncontrolled infection or medical condition that could interfere with the conduct of the study.
Test product, dose and mode of administration:	Dabrafenib (150 mg PO BID) and Trametinib (2 mg PO QD) in combination with Metformin (500 mg PO BID x 2 weeks, then 850 mg PO BID) until progression.
Reference therapy:	Dabrafenib and Trametinib without Metformin.
Duration of treatment:	
 • Pre-treatment phase: An up to 42-day Screening period for collection of Baseline assessments (scans prior to study enrollment may be used for baseline measurement); • Treatment phase: Treatment period of 28-day cycles until progression unless unacceptable toxicity; • Follow-up phase: Patients will be followed for survival for a period of up to 3 years.
Criteria for evaluation:	
Efficacy Assessments
 
Tumor response and disease progression will be determined by the Investigator using objective radiologic criteria (Investigator assessed review of CT scans). Disease response or progression will be determined according to RECIST 1.1. An MRI will be used only if CT scans are not appropriate or CT scan results are not conclusive.
 
Primary efficacy endpoint: RECIST 1.1 objective response rates
 
Secondary efficacy endpoint: Overall survival
 
Pharmacokinetic Not applicable.
 
Pharmacodynamic

Criteria for evaluation (continued):	Not applicable Safety Safety will be assessed by the monitoring and recording of all adverse events (AEs) and serious adverse events (SAEs), regular monitoring of hematology, blood chemistry, regular measurement of vital signs, and the performance of physical examinations.

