Signaling though the B-Raf oncogene in melanoma cells blocks the activation of AMPK^{23, 24}. by the kinase LKB1 and inhibition of B-Raf, like Metformin, caused activation of AMPK^{23, 24}. Perhaps not surprisingly, Metformin has been found to have significant pre-clinical activity in melanoma cells *in vitro* and *in vivo*, including: (i) causing a G2/M cell cycle arrest and apoptosis; (ii) mitochondrial membrane depolarization; (iii) induction of the p53 tumor suppressor; (iv) induction of autophagy; and (v) anti-tumor activity against the B16 syngeneic mouse model of melanoma²⁵. Additionally, the combination of the B-Raf inhibitor, Vemurafenib, with Metformin has been found to synergistically kill BRAF^{V600E}-positive melanoma cells *in vitro* (although certain highly resistant lines are marginally promoted by the combination)²⁶. Last, a phase I trial of the combination of a mTOR inhibitor, Temsirolimus (which has no efficacy against melanoma) with Metformin in 8 solid tumor patients, revealed a partial response in a single metastatic squamous cell carcinoma patient and stable disease in four patients, including a stage IV melanoma patient who experienced no progression for 22 months while on therapy (median overall survival is < 1 year)²⁷. **Based on these pre-clinical studies and phase I trial, we hypothesize that the combination of an FDA-approved non-toxic dose of oral Metformin with the B-Raf inhibitor, Dabrafenib, and the MEK inhibitor, Trametinib, will yield little toxicity and improve clinical outcomes in terms of objective response rates and survival in metastatic melanoma patients.** An important consideration for such a combination trial is the possibility that Metformin will decrease blood glucose concentration in non-diabetic patients and thus cause hypoglycemia and associated symptoms. *However, in a randomized trial of 166 non-diabetic men with hypertension, the fasting blood glucose (5.6 ± 0.74 mM) only dropped by 3% after three months of treatment with 850 mg PO BID of metformin (to 5.44 mM ± 0.83)²⁸.*

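### A pass under Table S1 shows a response rate above 64%, not that metformin adds to dabrafenib/trametinib: if the doublet's true rate is the cited 76% and metformin is inert, the rule still passes with probability 0.57

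*Combined protocol and SAP*

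**What the plan says.** Section 1.2 hypothesises that adding metformin to dabrafenib and trametinib will "improve clinical outcomes in terms of objective response rates and survival in metastatic melanoma patients". The synopsis gives the reference therapy as "Dabrafenib and Trametinib without Metformin". Section 6.1 describes a single-arm, uncontrolled trial, so the null rate is the only comparator inside the decision rule.

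Section 6.3 reports that "the objective response rate to Dabrafenib and Trametinib using RECIST 1.1 Criteria is 76% (N=54, 95% CI, 65% to 87" percent). It then states that "an objective response rate less than 64% should indicate the treatment is not sufficiently promising", which sets P0 = 0.64, and explains the choice: "this is a bit lower than the lower limit of the 95% CI". P1 is 0.80. Table S1 gives the two-stage limits: stop at 13 or fewer responses in 20, and reject the drug at 39 or fewer in 53. Success is therefore 40 or more of 53.

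Section 6.7 gives a different rule: 28 patients in the first stage, stop at 12 or fewer responses, then 25 more. It continues: "In order for the treatment to be declared effective there has to be objective responses in at least 29 patients". Its stated early-stopping chance is computed at a response rate of 41%.

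Section 6.5 plans to compare response rates with a 2011 publication, reference 8. Section 1.2 identifies that reference as the vemurafenib versus dacarbazine trial.

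**The concern.** The scientific question is what metformin adds to a doublet with a cited response rate of 76%. The decision rule tests against 64%, and its lowest passing result is 75.5%. A trial can pass with a response rate no better than the doublet's. Nothing in 6.3, 6.5 or 6.7 says how far a pass may be interpreted, and 6.7 attaches a verdict of effectiveness to it. A reader who knows the hypothesis in 1.2 would naturally take a pass as support for adding metformin. The planned comparison in 6.5 does not guard against this, because its comparator is not the doublet.

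**Working it through.** **Inputs.** From 6.3 and Table S1: P0 = 0.64, P1 = 0.80, n1 = 20, r1 = 13, n = 53, r = 39, alpha 0.05, power 80%. Doublet: 76%, N=54, CI 65% to 87%. From 6.7: continue with at least 13 of 28, succeed with at least 29 of 53.

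**Formulas.** For true rate p, with X1 responses in stage 1 and X2 in stage 2:
- early stop: PET(p) = P(X1 ≤ 13 | 20, p)
- expected size: 20 + (1 − PET) × 33
- pass: sum over x = 14 to 20 of P(X1 = x | 20, p) × P(X2 ≥ 40 − x | 33, p)

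**Reproducing Table S1.** At p = 0.64, PET = 0.6197 (plan: 0.62). Expected size = 20 + 0.3803 × 33 = 32.55 (plan: 33). Pass probability = 0.0467 (plan: alpha 0.05). At p = 0.80, pass probability = 0.8047 (plan: 80%). The table has been read as intended.

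**Reproducing 6.7.** At p = 0.41, the early-stop probability is 0.656 and the expected size 36.6, matching the 66% and 37 in that section. It is therefore a complete second design built on another null rate.

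**Pass probability under each rule.**

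| True response rate | Table S1: early stop | Table S1: pass | 6.7: pass |
|---|---|---|---|
| 64% (P0) | 0.620 | 0.047 | 0.931 |
| 65% (lower CI limit) | 0.583 | 0.063 | 0.949 |
| 70% | 0.392 | 0.218 | 0.992 |
| 76% (cited doublet rate) | 0.184 | 0.570 | 0.9997 |
| 80% (P1) | 0.087 | 0.805 | >0.999 |
| 87% (upper CI limit) | 0.010 | 0.985 | >0.999 |

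**What the smallest pass says about metformin.** Table S1 success begins at 40/53 = 75.5%. A rate of 76% in 54 patients corresponds to 41/54 = 75.9%.
- Difference: 0.7547 − 0.7593 = −0.0045, or −0.5 points.
- Standard error: √(0.7547 × 0.2453/53 + 0.7593 × 0.2407/54) = √(0.003493 + 0.003385) = 0.0829.
- 95% CI: −0.0045 ± 1.96 × 0.0829, or −16.7 to +15.8 points.

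The smallest passing result is compatible with a sizeable loss, no change, or a sizeable gain relative to the doublet.

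**Moving the null to 76% at the same size.** With n = 53, at least 46 responses would be needed (exact one-sided error 0.040), and power at 80% would be 0.14. At this size the trial cannot test P1 against the doublet's rate, so the remedy lies in the stated conclusion.

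**The case against.** The plan explains its choice of 64% openly, as a floor just below the doublet's lower confidence limit. Screening out a regimen clearly worse than the doublet is a legitimate aim for a single-arm phase II trial. Section 2.1 sets the phase II objective as the activity of the combined regimen, and no section says that passing Table S1 demonstrates metformin's contribution. All of this stands: P0 = 64% is a debatable design choice, not an internal error. It does leave the plan silent on what a pass means for the hypothesis in 1.2.

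The 57% also depends on 76% being the doublet's true rate here. That figure comes from 54 patients, the plan itself expects 60–80%, and the documents do not describe the cited study's population. A reader might infer that an inert metformin would pass more often than not in general. The documents do not support that: at a true doublet rate of 70% the probability is 0.22.

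A reader might also take the effectiveness wording in 6.7 to belong to the 57%. It does not. That wording occurs only in 6.7 and is tied to the 29-response rule, whose pass probability at 76% exceeds 0.999.

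Finally, 6.5 already plans confidence intervals and a comparison with published rates. That comparison uses the vemurafenib trial, and correcting the source would still leave the meaning of a pass unstated.

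**Conclusion.** The point holds in a limited form. Under Table S1, a pass supports the statement that the response rate exceeds 64%. It does not show that metformin contributes, because the rule can be met at 75.5%, below the 76% cited for the reference doublet. If the doublet's true rate in this population is 76% and metformin adds nothing, the pass probability is 0.57; over the cited CI it runs from 0.06 to 0.98.

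The 57% should not be read as the trial's type I error: against the null the plan chose, that error is 0.047 and is controlled. Nor is it an unconditional chance of a misleading result.

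The figure applies only if Table S1 governs. If 6.7 governs, the threshold is 29/53 = 54.7%, a pass occurs with probability 0.93 at a true rate of 64%, and even the claim of exceeding 64% fails.

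**What to change.** Keep N and P0.

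1. Reconcile 6.7 with Table S1 so that one decision rule governs. The changes below assume it is Table S1; their wording would be false under the present 6.7 rule.
2. In 6.7, replace the statement that the treatment is declared effective, and add the same sentence to 6.3: success means the objective response rate has been shown to exceed 64%, and this does not by itself show that metformin adds to dabrafenib/trametinib.
3. Add to Table S1 the pass probability at 76% (0.57), with its range over the cited CI (0.06 at 65% to 0.98 at 87%).
4. In 6.5, report the difference from the published doublet rate of 76% (N=54) with a 95% CI carrying the sampling error of both studies. Label it a descriptive cross-study comparison that does not remove population differences.

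The cost is some wording, one table entry and one interval. No patients are added. The downside for the sponsor is that the stated claim becomes less favourable.

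### Section 6.5 puts every covariate, age included, into groups with cut-offs not fixed in advance; this loses power, leaves room for outcome-driven cuts, and sparse levels can leave the response model without finite estimates

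*Combined protocol and SAP*

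**What the plan says.** The third secondary objective (section 2) is to explore covariate effects on objective response, toxicity and overall survival. Section 6.5 covers it in two places.

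- Under the general approach it names four factors (ethnicity, gender, age and pathological subtype) and adds: "The various factors will be placed into categorical variables". Prognostic factors for survival are to be examined with "Cox proportional hazards regression models in both uni-variable and multi-variable setting".
- Under the secondary objectives it says: "We will identify the covariates and define specific groups, using some cut-offs, that are meaningful in a regression analysis". Response and toxicity then go into a logistic regression, and survival into a Cox model.

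No cut-off value appears anywhere. Nor does the plan say when cut-offs will be set, how many covariates may enter, or what will be done with sparse levels or non-finite estimates. On sample size, section 6.3 says "we plan to enroll a maximum of 53 patients".

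**The concern.** Three separate problems follow, and they differ in how firmly the text supports them.

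1. **Lost power.** This follows directly from the instruction to categorise. A real age effect is harder to see once age is split into groups.
2. **Cut-offs left open.** A cut-off not written down beforehand can be picked after the outcomes are known. A search of that kind produces prognostic factors that are not real.
3. **Sparse levels in the response model.** The response rate is expected to be high, so non-responders are few. A factor level with no non-responder, or no responder, has an infinite ordinary odds ratio.

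At stake is whether the covariate results can be interpreted. The efficacy decision does not depend on them.

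**Working it through.** **Inputs from the plan.** N = 53, P0 = 0.64, P1 = 0.80, and 76% as the published response rate (section 6.3); a toxicity rate of 33% (section 6.8); follow-up of up to 3 years (section 6.4). The plan gives no figure for the covariate models. The design that supplies N does reproduce: stopping at 13 or fewer responses in 20 and rejecting at 39 or fewer in 53 gives alpha 0.0467, power 0.805, early termination 0.620 and expected N 32.6 at 64% (Table S1: 0.05, 80%, 0.62 and 33).

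**Which count limits which model.**
- Response: non-responders = 53 × (1 − p). This is 53 × 0.20 = 10.6 at 80%, 53 × 0.24 = 12.7 at 76%, and 53 × 0.36 = 19.1 at 64%.
- Toxicity: 53 × 0.33 = 17.5 events at the stopping rate.
- Survival: deaths by 36 months = 53 × (1 − 2^(−36/m)) for exponential survival with median m. For m = 6.2 months (the historical stage IV figure in section 1.1) this is 52.1. For an assumed m = 24 it is 34.3.

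**Power lost to a median split.** Simulation at n = 53, two-sided 5%, with assumed odds ratios per SD of 2.0 and 2.5 (log-odds 0.69 and 0.92, either side of 0.8):

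| Response rate | OR per SD | Continuous | Median split | Loss (points) |
|---|---|---|---|---|
| 64% | 2.0 | 61% | 44% | 17 |
| 64% | 2.5 | 83% | 64% | 19 |
| 80% | 2.0 | 49% | 34% | 15 |
| 80% | 2.5 | 68% | 50% | 18 |

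At a log-odds of exactly 0.8 and 76% response, two runs gave 65% against 49% and 61% against 41%. The losses run from about 15 to 21 points.

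**False positives, covariate with no effect, n = 53.** One fixed median cut: 4.9-5.8%. Best of three quartile cuts: 12-18%. Best of all inner cuts: 35-47%. Score tests give the lower end of these ranges and likelihood-ratio tests the upper end.

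**Non-finite estimates, response model, one binary factor.** For a level of prevalence q with no effect, the chance that the level lacks a non-responder or lacks a responder is close to

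(1 − q(1−p))^53 + (1 − qp)^53 − (1 − q)^53.

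- q = 0.10, p = 0.80: 0.343 + 0.012 − 0.004 = 0.351.
- q = 0.10, p = 0.64: 0.143 + 0.030 − 0.004 = 0.169, or 0.170 before rounding the terms.
- The same formula gives 2-12% at q = 0.20 and 49-64% at q = 0.05. At q = 0.50, counting empty cells in either group, it is under 1%.

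**Non-finite estimates, response model, the four named factors together.** Simulation at n = 53. All group frequencies are assumptions:

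| Assumed ethnicity minority; subtype split | 64% | 76% | 80% |
|---|---|---|---|
| 20%; 50/50 | 2% | 6% | 13% |
| 20%; 60/40 | 2% | 8% | 16% |
| 20%; 50/30/20 | 4% | 17% | 25% |
| 10%; 50/30/20 | 18% | 33% | 43% |
| 8%; 55/20/15/10 | 40-44% | 62-63% | 71-78% |
| 5%; 50/25/15/10 | 55% | 70% | 78% |

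With Firth's penalised likelihood on six-parameter designs of the 8% row's kind, every estimate stayed finite (largest absolute log-odds about 5). A simple iteration missed strict convergence tolerance in 6-8% of runs.

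**The case against.** The best defence is that this is an exploratory objective on which nothing turns. The response-rate test and the futility and safety rules make no use of it. Of the four named factors only age clearly needs a cut-off; the other three are categories by nature. All of this stands, and it keeps the point minor. It does not remove it, because categorising age is an explicit instruction and the text leaves room for further covariates.

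Three stronger readings are tempting, and the documents do not support them.

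- A reader might infer from "We will identify the covariates and define specific groups, using some cut-offs, that are meaningful in a regression analysis" that cut-offs will be searched against outcome. The sentence does not say so; groups that are meaningful in a regression could equally be set on clinical grounds. The inflated false-positive rates are therefore conditional.
- A reader might apply the 11 to 19 non-responders to all the models. They limit only the response model; the Cox model depends on deaths and the toxicity model on toxic events.
- A reader might conclude that the models will often fail and the objective will yield nothing. Failure depends on group sizes that the documents do not give, and multivariable fitting is stated only for Cox. Even with the 8% and 55/20/15/10 frequencies, the sex and age coefficients were non-finite in at most 1.5% of trials. The trouble sits in the rare levels, about which little could be learned by any method.

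**Conclusion.** The point holds in limited form. The loss of about 15 to 21 points of power follows from the plan's own instruction, given a roughly linear effect near 0.8 log-odds per SD and a median split. Among the named factors it concerns age. The rise in false positives from 5% to 12-18% or 35-47% is a risk that the wording leaves open, not something the plan commits to. Non-finite estimates in the response model range from about 2-16% of trials with balanced or two-level groups to 40-78% with sparse groups, with moderately sparse groups in between. All of these rest on N = 53 and on assumed frequencies. The working gives no basis for a fixed cap on the number of factors or for penalised estimation in the Cox model. This is a low-cost improvement to a secondary, exploratory analysis.

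**What to change.** In section 6.5, replace "The various factors will be placed into categorical variables" with wording that does two things:

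- keeps age and any other continuous covariate continuous in the logistic and Cox models;
- requires any grouping that is still needed, such as merging rare subtypes, to be written down with its cut-offs before outcome data are reviewed.

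Amend the covariate paragraph under the secondary objectives to match. For the objective-response model, state that Firth's penalised likelihood or an exact method will be used where a level is sparse or ordinary estimates are not finite. The plan names SAS but no procedure, so the method and its convergence settings should be named.

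The cost is a few sentences and a programming choice. Penalised estimates are slightly shrunken, and a continuous term assumes a roughly linear effect on the model's scale. Sample size, data collection and the primary analysis do not change.

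### Section 6.7 gives a Phase II stopping and success rule that contradicts Table S1; followed as written, it declares a 64% response rate effective 93% of the time instead of about 5%

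*Combined protocol and SAP*

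**What the plan says.** Section 6.3 (Sample Size, Phase II) sets the null rate: "Therefore an objective response rate less than 64% should indicate the treatment is not sufficiently promising". The target rate is 80%, with alpha 0.05 and power 80%. On the design it says: "Using Simon's two stage minimax design for phase II trials we plan to enroll a maximum of 53 patients". It then says: "In first stage, 20 patients will be enrolled". Table S1 puts the first-stage rejection limit at 13 responses. The row labelled "Upper Limit for 2 nd Stage Rejection of Drug" gives 39, so success needs 40 of 53. The table states an expected sample size of 33 and an early termination probability of 0.62, both at a response rate of 0.64.

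Section 6.7 (Futility) covers the same three-drug regimen. Its interim rule reads: "in the first stage we will enroll 28 participants and if we observe at most 12 objective responses", no further patients are enrolled. With 13 or more responses, 25 more patients are added. The success rule is: "In order for the treatment to be declared effective there has to be objective responses in at least 29 patients". Its operating characteristics are given as: "If the objective response rate is only 41%, we will have 66% chance of stopping the study early and, at most, 37 patients".

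**The concern.** The two sections differ in first-stage size (20 or 28), interim limit (13 or 12), final limit (success at 40 or at 29) and the rate at which properties are quoted (64% or 41%). They share only the maximum of 53, and the documents do not say which section prevails.

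Section 6.7 is the only place where the rule is written out as an instruction on when to halt accrual and when to call the regimen effective, so a study team may well follow it. Its success bar, 29/53 = 54.7%, lies below the 64% that Section 6.3 treats as too low to be of interest. In a single-arm trial with no concurrent control, a positive declaration on that bar would say almost nothing about a gain from adding metformin.

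Two printed rules also leave room to choose between them after the data are seen. A final count of 29 to 39 responses is a success under Section 6.7 and a failure under Table S1. Thirteen responses in the first 20 patients end accrual under Table S1 but already satisfy the Section 6.7 condition for continuing.

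**Working it through.** **Inputs.** From Section 6.3 and Table S1: P0 = 0.64, P1 = 0.80, n1 = 20, r1 = 13, n = 53, r = 39. From Section 6.7: n1 = 28, r1 = 12, n = 28 + 25 = 53, r = 28 (success at 29 or more), properties quoted at 0.41. Here r1 and r are the largest counts that still reject the drug.

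**Formulas**, for true response rate p:

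- Early termination: PET = P(X1 ≤ r1), with X1 ~ Bin(n1, p).
- Expected size: E[N] = n1 + (1 − PET)(n − n1).
- P(effective) = Σ over x > r1 of P(X1 = x) · P(X2 ≥ r + 1 − x), with X2 ~ Bin(n − n1, p).

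**Step 1: reproduce Table S1.** At p = 0.64, PET = P(Bin(20, 0.64) ≤ 13) = 0.6197 (stated 0.62). E[N] = 20 + 0.3803 × 33 = 32.55 (stated 33). Type I error is 0.0467. At p = 0.80, power is 0.8047. Reading the limits as not inclusive (stop at 12 or fewer, success at 39) gives PET 0.436 and type I error 0.088, so the inclusive reading is the intended one.

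**Step 2: reproduce the figures in Section 6.7.** At p = 0.41, PET = P(Bin(28, 0.41) ≤ 12) = 0.6557 (stated 66%). E[N] = 28 + 0.3443 × 25 = 36.6 (stated 37). P(effective) = 0.029. The figures therefore fit a null of 41%, a rate that Section 6.3 does not use. The 37 is an average: under this rule the actual number treated is either 28 or 53.

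**Step 3: put both rules at the plan's own null, p = 0.64.**

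| Quantity at 64% | Table S1 | Section 6.7 |
|---|---|---|
| P(declared effective) | 0.047 | 0.931 |
| P(early stop) | 0.620 | 0.018 |
| E[N] | 32.6 | 52.5 |
| Success bar | 40/53 = 75.5% | 29/53 = 54.7% |

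For Section 6.7, E[N] = 28 + 0.9819 × 25 = 52.5. A simulation of 2,000,000 trials also gave P(effective) = 0.931. The size of the result is no surprise: at 64% the expected counts are 28 × 0.64 = 17.9 at the interim and 53 × 0.64 = 33.9 at the end, both well above the limits of 12 and 28. Even at a true rate of 55%, Section 6.7 declares success with probability 0.561.

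**Step 4: mixed readings at p = 0.64.**

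- Table S1 interim (20/13) with success at 29: type I error 0.378.
- Section 6.7 interim (28/12) with success at 40: type I error 0.052, early stop 0.018.

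Neither mixture keeps the 5% error rate, and the second loses nearly all futility stopping.

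**The case against.** The best reply is that Table S1 also states rejection limits for both stages, so Section 6.7 is not the sole decision rule and the 93% arises only if staff follow it and disregard the table. That stands as a qualification. The false-positive rate is not fixed by the document: it is 4.7%, 5.2%, 37.8% or 93.1%, depending on which limits are applied. It does not remove the defect, because a decision rule whose error rate depends on the page consulted is not prespecified.

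Section 6.5 also reports the response rate with a 95% confidence interval, so a reader would see the estimate whatever the declaration. This softens the harm to interpretation but does nothing for the accrual decision.

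Table S1 is not beyond question either. Section 6.3 calls the design minimax, but an exact search finds a smaller one for the same inputs: stop at 14 or fewer of 22, reject at 37 or fewer of 50, type I error 0.0472, power 0.8001. Table S1 still meets its stated alpha and power and keeps the planned 53, so it remains the natural default. Of the two printed rules it is the only one that fits the stated hypotheses.

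Finally, that Section 6.7 was carried over from a design for another null rate is an inference from the match at 41%. The contradiction does not depend on it.

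**Conclusion.** The concern holds and must be fixed before any first-stage decision. The two sections give incompatible rules for the primary endpoint. If Section 6.7 is followed in full, the probability of declaring the regimen effective at P0 = 64% is 93.1% instead of 4.7%, and the probability of stopping early is 1.8% instead of 62.0%. On average 52.5 − 32.6, or about 20, more patients would be treated at a response rate the plan itself regards as inadequate, contrary to the aim in Section 6.6 of limiting exposure to an ineffective treatment.

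These figures assume independent responses with a common rate, all enrolled patients counted in the denominator, and each rule applied exactly as printed. The limits in Table S1 are read as inclusive, the reading that reproduces its own 0.62.

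**What to change.** Rewrite Section 6.7 to match Table S1, after the sponsor confirms that Table S1 is the intended design:

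- Enrol 20 patients in the first stage; stop accrual if 13 or fewer have an objective response.
- With 14 or more, enrol 33 further patients, for a total of 53.
- Declare the regimen effective only with 40 or more responses among 53.
- Replace the quoted properties with: at a response rate of 64%, early stopping probability 62%, expected sample size 33, maximum 53.

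In the same amendment, either drop the word minimax from Section 6.3 or state why 53 was kept although a 50-patient design meets the same error rates.

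The cost is a protocol amendment. It adds no patients, procedures or analyses. Compared with Section 6.7 as printed, it moves the interim look from 28 to 20 patients, so it should be in place before the 20th patient is evaluated. If accrual has already passed that point, the sponsor should document how the interim decision will be made before looking at the response count.
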